7.3 Check In Phone Calls (Visits 3 & 4)

Study staff will call participants at 2 days (± 1 day) and 5 days (± 1 day) from the start of the arm. Phone contacts will be made according to the contact window, regardless of the day of the week.

Study staff will:

- Review any adverse events or device issues experienced
- Answer any questions the participant may have
- Bionic Pancreas arm:
 - Review glucose control
 - Review study policies and procedures related to glucose management and inquire about any hypoglycemic or hyperglycemic events
 - Review any need for a change in the glucose target setting
 - Assess the participant’s ability to follow the protocol and use the device

Study staff may also contact participants in the usual care arm using the Dexcom G6 Pro CGM sensor 10 days after sensor placement, to remind them to replace the study sensor if they haven’t already and provide assistance as needed.

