12. Participant Compensation	36
13. References.....	37
14. Appendices.....	40
14.1 Appendix A: Prior Studies Conducted Using the Bionic Pancreas System	40
14.1.1 Studies Conducted with the iPhone-Based BP System.....	40
14.1.2 Studies Conducted with the Gen 3 iLet Bionic Pancreas System.....	46
14.2 Appendix B: Psychosocial questionnaires	49
14.3 Appendix C: Hyperglycemia treatment plan.....	51

Abbreviations	
ADA	American Diabetes Association
BG	Blood Glucose
BHBP	Bihormonal Bionic Pancreas
BMI	Body Mass Index
BP	Bionic Pancreas
BU	Boston University
CF	Cystic Fibrosis
CFRD	Cystic Fibrosis Related Diabetes
CFTR	Cystic fibrosis transmembrane conductance regulator
CGM	Continuous Glucose Monitor
CHF	Congestive Heart Failure
DPP-4	Dipeptidyl peptidase-4
FDA	Food and Drug Administration
FEV1	Forced Expiratory Volume in 1 second
GLP-1	Glucagon-like peptide-1
GUI	Graphical User Interface
HCG	Human Chorionic Gonadotropin
IOBP	Insulin-only Bionic Pancreas
IRB	Institutional Review Board
ISO	International Organization for Standardization
IUD	Intrauterine device
IV	Intravenous
MDI	Multiple Daily Injections
OCP	Oral Contraceptives
PK	Pharmacokinetics
RDA	Recommended Dietary Allowances
SC	Subcutaneous
SGLT-2	Sodium-glucose co-transporter-2
T1D	Type 1 Diabetes
T2D	Type 2 Diabetes
TIA	Transient Ischemic Attack
UC	Usual Care
UI	User Interface

Table 1. Abbreviations

Visit Procedures	Screening	Start Visit	Check In Call 1	Check In Call 2	Crossover Visit	Check In Call 3	Check In Call 4	Final Visit
Days from start visit (window):		0	2 (± 1)	5 (± 1)	14* (+2)	16# (± 1)	19# (± 1)	28# (+2)
Informed Consent	X							
Eligibility Assessment	X							
Height	X							
Weight	X	X			X			X
Urine pregnancy test	X	X			X ¹			
Adverse Event querying		X	X	X	X	X	X	X
Psychosocial questionnaires			X		X			X
Sputum collection		X			X ²			X ²
CGM insertion		X			X ³			
iLet initiation		X ⁴			X ⁴			
Data download					X			X

* visit may be split into separate shutdown and start up visit; start up visit must occur within 14 days of shutdown visit
may differ based on length of window between study arms

1 if separate startup visit occurs 14 days after shutdown visit
2 if sputum wasn't collected at start visit and this is the next in person visit
3 if applicable, based on randomization
4 as needed

Table 2. Visit Procedures

1. Background and Significance

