7.4 Crossover Visit (Visit 5)

- This visit will occur 14 (+2) days from the start of the first arm. This visit will serve as the shutdown visit for the first arm and the startup visit for the second arm of the study.
- Participants will return to the clinic and answer the post questionnaires for the study arm or will complete the study visit virtually via Zoom.
- The body weight of the participant will be documented.
 - *If the visit is conducted virtually, the participant will measure body weight at home and a verbal report of their weight will be acceptable.*
- Study devices will be downloaded as applicable (CGM, glucometer, InPen, iLet).
 - *If the visit is conducted virtually, device downloads may be skipped. Participants will ship the iLet back to the study site using provided shipping materials for later downloading.*
- Study staff will review any changes in the participant’s medical history or medications to ensure continued eligibility and will document any adverse events that may have occurred since their last study visit.

- Study staff will specifically ask participants if they had any infusion site or CGM sensor site reactions or other skin irritation during the arm and will document any reactions.
 - Any changes to medications or medical history and any adverse events that may have occurred since their last study visit will be documented.
- Study staff will review all study procedures and policies (including the use of the Dexcom and Contour Next One, and the iLet) and the upcoming visit schedule.
- If the participant is switching to the iLet bionic pancreas arm:
 - The participant will remove their Dexcom G6 Pro sensor if applicable. The participant will a Dexcom G6 CGM sensor if necessary.
 - Study staff will supervise the setup of the insulin cartridge and infusion set.
 - The control algorithm will be initialized with the participant's current weight.
 - The participant's own insulin infusion pump will be stopped and disconnected, and its infusion set will be removed. For participants using multiple daily injections of insulin, they will take their insulin as usual prior to starting the bionic pancreas, then stop taking any insulin other than delivered by the bionic pancreas once it is started.
 - Study staff will verify that the iLet bionic pancreas is functioning properly prior to ending the study visit.

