- Any medical advice needed by the participants during their participation, which is not directly related to BG control during the experiment, should be obtained by them in the usual manner with

their primary care physician, pulmonologist, or endocrinologist.

- If a participant develops an illness during the experiment, they can seek medical care as usual. As long as the participant is not hospitalized, the study can be continued. If the participant is unable to eat for a period exceeding one day, they must notify study staff so that the medical staff can assess the safety of continuing in the study.
 - If a participant requires hospitalization during the experiment, they will discontinue the experiment and their participation in that study arm will end. The data collected up to their admission will not be used for the primary glycemic analysis but will be used in safety analyses. The participant can restart the study arm 2 weeks after discharge, but no later than 4 weeks after discharge.
- If a participant has exacerbation requiring oral glucocorticoid therapy, they can continue with all study arms as long as they do not require hospital admission.
- Participants may participate in any activities that they wish, as long as they abide by the policies above.
- There are no restrictions of any kind on diet or exercise, although participants should attempt to maintain similar dietary habits and exercise habits during each arm of the study. The iLet bionic pancreas must be kept dry during exercise.
- Participants may choose to withdraw from the study at any time. If they withdraw from the study, they should contact a provider immediately. If they are wearing the bionic pancreas, a provider will help them transition to their own insulin regimen safely. If the participant wishes to discontinue use of the bionic pancreas but is willing to continue in the study, they will be asked to continue to wear the Dexcom G6 CGM for the entire study period and complete the study visits to facilitate full data collection and analysis by the intention to treat principle.
- Participants will be asked to report all hypoglycemia, carbohydrate interventions, any adverse events, time spent exercising, any unscheduled infusion set changes, alcohol use, and other questions through a daily email survey.

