Whenever a participant is sent to the emergency department, study staff must confirm that the participant has arrived at ED within an hour, and study staff member should speak with a member of the medical staff at the emergency department to confirm arrival and provide information about the reason for referral to the ED.

If a participant cannot be reached and there is concern for their wellbeing (e.g. if their Clarity data shows

hypoglycemia or severe hyperglycemia) then study staff should attempt to reach close contacts. If no contacts are available or their contacts do not succeed in reaching them quickly, then 911 should be called and a well-being check should be requested. Study staff must follow up on and document the results of the well-being check.

8. Biostatistical Analysis

8.1 Data Collected During Study Arms:

- CGM glucose (CGM glucose) every five minutes from the Dexcom CGM
- CGM data sufficiency (percentage of possible CGM values captured)
- All fingerstick BG measurements taken by the participant (meter download)
- Information collected from the daily email survey and phone calls including hypoglycemia, carbohydrate interventions, any other adverse events, any unscheduled infusion set changes or Dexcom CGM sensor changes.
- Insulin total daily dose (from the bionic pancreas, insulin pump download, or InPen)
- Timing of meal announcements and size of meals announced (in the bionic pancreas arm)
- Data from a questionnaire about attitudes and expectations regarding the bionic pancreas at baseline and on day 14 of each arm.
- Time under bionic pancreas control with CGM data in bionic pancreas arm
- Time under bionic pancreas control without CGM data in bionic pancreas arm
- Percent of time not under bionic pancreas control during the bionic pancreas arms
- List of technical faults associated with the bionic pancreas including cause and resolution
- Body weight after each arm

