8.2 Outcomes

Study endpoints will be calculated for days 3 – 14 so that any long-acting insulin on board has time to clear and therefore does not affect study outcomes. Adverse events will be reported for the entire study period.

The primary analysis of the designated endpoints will be calculated on an intention-to-treat basis, including data from periods when the bionic pancreas was not in use, if available (Dexcom CGM data may not be available in some failure modes). In cases where an arm was not completed, we will use the available data from that arm in the data analysis. We will calculate percentages, means and standard deviations or medians and interquartile ranges as appropriate. We will use paired t-test for comparison of means for normally distributed data and the Wilcoxon signed rank test for non-normally distributed data. We may, in exploratory analyses, also stratify participants for secondary analyses of the pre-specified endpoints by participant characteristics including: sex, age, use of CGM in usual care, baseline A1c, usual care insulin total daily dose, body mass index, FEV1, CFTR genotype, and/or number of CF exacerbations in the preceding year. Given the potential difference in glucose variability, participants under the age 18 will also be analyzed separately from the adult cohort.

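### Check-in calls ask specifically about low and high glucose events only in the iLet arm: a minor, avoidable difference in how adverse events are collected

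*Combined protocol and SAP*

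**What the plan says.** Section 7.3 (first arm) and Section 7.5 (second arm) schedule calls 2 and 5 days after the start of the arm, each with a window of one day either side. Two items apply to every participant: "Review any adverse events or device issues experienced", and answering questions. A further list applies only to the bionic pancreas arm. It covers glucose control, the target setting, ability to use the device, and this item: "Review study policies and procedures related to glucose management and inquire about any hypoglycemic or hyperglycemic events". The only addition for usual care is an optional reminder to replace the study sensor.

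Other parts of the plan bear on this:

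- Table 2 has a row for "Adverse Event querying", marked at every visit and call after screening, whichever arm is in progress.
- Section 7.7, under policies for both arms, has participants use a daily email survey to "report all hypoglycemia, carbohydrate interventions, any adverse events, time spent exercising, any unscheduled infusion set changes, alcohol use, and other questions".
- Section 8.1 lists among the data collected: "Information collected from the daily email survey and phone calls including hypoglycemia, carbohydrate interventions, any other adverse events". It does not limit this to one arm.
- Sections 7.4 and 7.6 require adverse events since the last visit to be documented at the end of each arm. On one event type they go further in both arms: "Study staff will specifically ask participants if they had any infusion site or CGM sensor site reactions".
- Section 8.2 states "Study endpoints will be calculated for days 3 – 14" and "Adverse events will be reported for the entire study period".

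**The concern.** Participants and staff know which arm is in progress, and each participant serves as their own control. A specific question tends to bring out more reports than a general one. If staff ask directly about low and high glucose on iLet calls but only about adverse events in general on usual-care calls, reported glycemic events may be somewhat higher on the iLet even when the true rates are equal.

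Some differences in detection follow from the device or from safety needs: iLet glucose alarms, ketone checks with notification of staff, and blinded sensors for usual-care participants who do not wear the Dexcom G6. The call question is different, because it can be made the same in both arms without loss. What is at stake is the between-arm comparison of non-severe glycemic adverse events, which the plan reports over the whole study period.

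**Working it through.** The plan gives no figure on this point to reproduce. The check is a comparison of text, followed by an illustration of scale.

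**Step 1: the call content by arm (7.3 and 7.5)**

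| Item | iLet | Usual care |
|---|---|---|
| General adverse event and device review | yes | yes |
| Answer questions | yes | yes |
| Specific question on low or high glucose events | yes | no |
| Glucose control, policies, target, device use | yes | no |

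The difference is a specific prompt against a general one. It is not contact against no contact.

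**Step 2: which outcomes the prompt can reach**

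- *Primary and secondary outcomes (8.2.1, 8.2.2):* all come from CGM. No effect.
- *Symptomatic hypoglycemia and carbohydrate treatment (8.2.3.2):* both are defined by daily participant reports, and 7.7 collects these identically in both arms. No effect as defined.
- *DKA and severe hypoglycemia (8.2.3.3):* these are major events, also covered by the daily survey, the general review and the end-of-arm visit. An effect is very unlikely.
- *Non-severe glycemic events reported as adverse events:* calls are a named source (8.1), so an effect is possible. Hyperglycemia has the least backup, because the survey list in 7.7 does not name it. However, the plan has no reported-hyperglycemia endpoint.

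**Step 3: illustration for hypoglycemia reported as adverse events**

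Let f be the share of the arm reached by the second call, p the share of events captured by the daily survey, q the share of missed events recovered by the specific prompt, and r the share recovered by the general review.

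- iLet capture: A = p + f(1 − p)q
- Usual-care capture: B = p + f(1 − p)r
- Excess on the iLet at equal true rates: A/B − 1

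Only f comes from the documents: 5 of 14 days, or 0.357. The rest are assumptions: p from 0.7 to 0.9, q from 0.5 to 1, and r at 50% to 80% of q.

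| p | q | r | A | B | Excess |
|---|---|---|---|---|---|
| 0.9 | 0.5 | 0.40 | 0.9179 | 0.9143 | 0.4% |
| 0.9 | 0.5 | 0.25 | 0.9179 | 0.9089 | 1.0% |
| 0.7 | 1.0 | 0.80 | 0.8071 | 0.7857 | 2.7% |
| 0.7 | 1.0 | 0.50 | 0.8071 | 0.7536 | 7.1% |

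**Step 4: what the illustration leaves out**

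The end-of-arm adverse event review takes place in both arms. If it recovers a share v of the events still missed, the excess becomes (1 − v)(A − B) / [B + v(1 − B)]. This is smaller than A/B − 1 for any v above zero, and it vanishes at v = 1. On their own assumptions, the figures in Step 3 are therefore upper-end values.

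**The case against.** The strongest reply is that the plan already handles this. The only participant-reported hypoglycemia count rests on a daily survey that names hypoglycemia in both arms. The general review probably covers it too: the 8.1 entry, "Information collected from the daily email survey and phone calls including hypoglycemia, carbohydrate interventions, any other adverse events", appears to treat hypoglycemia as one adverse event among others. End-of-arm visits give a further look in both arms. The iLet-only placement also has a purpose, since Section 6 makes changes of glucose target depend on hypoglycemia, while usual care involves no such study decision. Any bias would count against the investigational device.

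Most of this stands, and it is why the point is minor. It does not justify leaving the question out of usual-care calls. Staff can gather what they need for target decisions and still ask both arms, and the plan already asks about site reactions that way.

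A reader might infer something stronger: that the reported hypoglycemia outcome itself is biased. Suppose call reports were merged into the days 3–14 count, so that f = 3/12, and the usual-care review recovered nothing. With p = 0.7 and q = 1 the excess would be (0.7 + 0.25 × 0.3)/0.7 − 1 = 10.7%. The documents do not support this. Section 8.2.3.2 ties the count to daily reports, no merging rule is stated, and zero recovery conflicts with the adverse event review that usual-care calls do include.

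**Conclusion.** The difference is real, appears in both periods, and is avoidable. Its reach is narrow: it could slightly raise reported non-severe glycemic adverse events in the iLet arm. No formal efficacy conclusion depends on it.

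The size cannot be estimated from the documents, which give no capture or recovery rates. The 0.4% to 7.1% range rests wholly on the assumed rates, on equal true event rates, and on no recovery at the end-of-arm visit. It should be read as an upper-end illustration rather than an estimate. The direction rests on the general expectation that specific prompts yield more reports than general ones.

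**What to change.** In Sections 7.3 and 7.5, split the bullet. Move the question about hypoglycemic or hyperglycemic events into the list asked of every participant, and keep the policy review, glucose control, target setting and device-use items under the bionic pancreas arm.

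The cost is one extra question on each of the two existing usual-care calls: 2 × 30 = 60 questions for 30 completers (20 adults and up to 10 pediatric participants). No visit or call is added, and nothing is taken from iLet oversight. Priority is low.

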7.4 Crossover Visit (Visit 5)

- This visit will occur 14 (+2) days from the start of the first arm. This visit will serve as the shutdown visit for the first arm and the startup visit for the second arm of the study.
- Participants will return to the clinic and answer the post questionnaires for the study arm or will complete the study visit virtually via Zoom.
- The body weight of the participant will be documented.
 - *If the visit is conducted virtually, the participant will measure body weight at home and a verbal report of their weight will be acceptable.*
- Study devices will be downloaded as applicable (CGM, glucometer, InPen, iLet).
 - *If the visit is conducted virtually, device downloads may be skipped. Participants will ship the iLet back to the study site using provided shipping materials for later downloading.*
- Study staff will review any changes in the participant’s medical history or medications to ensure continued eligibility and will document any adverse events that may have occurred since their last study visit.

- Study staff will specifically ask participants if they had any infusion site or CGM sensor site reactions or other skin irritation during the arm and will document any reactions.
 - Any changes to medications or medical history and any adverse events that may have occurred since their last study visit will be documented.
- Study staff will review all study procedures and policies (including the use of the Dexcom and Contour Next One, and the iLet) and the upcoming visit schedule.
- If the participant is switching to the iLet bionic pancreas arm:
 - The participant will remove their Dexcom G6 Pro sensor if applicable. The participant will a Dexcom G6 CGM sensor if necessary.
 - Study staff will supervise the setup of the insulin cartridge and infusion set.
 - The control algorithm will be initialized with the participant's current weight.
 - The participant's own insulin infusion pump will be stopped and disconnected, and its infusion set will be removed. For participants using multiple daily injections of insulin, they will take their insulin as usual prior to starting the bionic pancreas, then stop taking any insulin other than delivered by the bionic pancreas once it is started.
 - Study staff will verify that the iLet bionic pancreas is functioning properly prior to ending the study visit.
 - The participant will be asked to demonstrate their competency by placing at least one practice infusion site and one site in themselves and "teach back" to confirm that they adequately understand when to replace a set. Study staff will be trained that participants who have not previously used an insulin pump or who have not previously used the study infusion set may need additional time for training on pump-related tasks, such as placement of infusion sets and how to recognize when an infusion set needs to be replaced.
 - Study start visits for participants who may need more assistance with the infusion set, and/or participants who live alone should be scheduled early in the day so that there is sufficient time before bedtime to recognize if the first infusion set is not performing well. Study staff may follow up with participants that need additional support before the end of the first day to confirm everything is working and the participant is comfortable.
- If the participant is switching to the Usual Care arm, a provider will review the last several hours of insulin dosing and glucose trend data and assist the participant in resuming their usual care.
 - The participants will place a Dexcom CGM sensor and study staff will confirm they are doing it properly.
 - If participants use a Dexcom G6 CGM as part of their standard care, they will continue to use the Dexcom G6 CGM during the Usual Care arm.
 - If the participant does not use a CGM, or uses a different type of CGM, they will use the Dexcom G6 Pro CGM during the Usual Care arm.
- All participants will be given additional supplies as needed.
- It is preferred that the second arm be started at this visit. If that is not possible, then the startup for the second arm may be delayed up to 14 days, during which participants will revert to their own usual care. An additional visit will be scheduled for the startup of the second arm. If the startup is delayed the full 14 days, a urine pregnancy test will be repeated at this additional visit.

7.5 Check In Phone Calls (Visits 6 & 7)

Study staff will call participants at 2 days (± 1 day) and 5 days (± 1 day) from the start of the arm. Phone contacts will be made according to the contact window, regardless of the day of the week.

Study staff will:

- Review any adverse events or device issues experienced
- Answer any questions the participant may have

- Bionic Pancreas arm:
 - Review glucose control
 - Review study policies and procedures related to glucose management and inquire about any hypoglycemic or hyperglycemic events
 - Review any need for a change in the glucose target setting
 - Assess the participant's ability to follow the protocol and use the device

Study staff may also contact participants in the usual care arm using the Dexcom G6 Pro CGM sensor 10 days after sensor placement, to remind them to replace the study sensor and provide assistance as needed.

